5.1.2. Apremilast-exposure Period for Safety Analysis

In addition to the above defined phases, Apremilast-exposure Period will be used for safety analyses.

- Apremilast-exposure Period:

This period starts on the date of either: (1) the first dose of IP following randomization (Week 0/Visit 2) for subjects who are treated with apremilast 30 mg BID first; or (2) the first dose of IP from the IP dispensed at Week 16/Visit 7 for subjects who were originally treated with placebo and are treated with apremilast 30 mg BID at Week 16.

This period stops on either: (1) data cut-off date; or (2) the day of the treatment discontinuation if the subject discontinued prior to or at Week 32/Visit 10; or (3) the last

known study day if the subject lost to follow-up prior to Week 32/Visit 10; or (4) Week 32/Visit 10 visit date.

5.2. Definition of analysis populations

5.2.1. Intent-to-treat Population

The intent-to-treat (ITT) population will consist of all subjects who are randomized. Subjects will be included in the treatment group to which they are randomized.

5.2.2. Per-protocol Population

The per protocol (PP) population will consist of all subjects included in the ITT population who receive at least one dose of IP, have both baseline and at least one post-treatment ScPGA evaluation, and have no important protocol deviations which may affect analyses in the Placebo-controlled Phase.

5.2.3. Safety Population

5.2.3.1. Placebo-controlled Phase (Weeks 0 to16)

Safety analyses will be based on the safety population, which will include all subjects who are randomized and receive at least one dose of IP. Subjects will be included in the treatment group corresponding to the IP they actually received (apremilast 30 mg BID or placebo) for the analyses and summaries using the safety population.

5.2.3.2. Apremilast Extension Phase (Weeks 16 to 32)

Safety analyses will be based on subjects who are treated in the phase. At Week 16, subjects will continue 30 mg BID treatment or will switch to 30 mg BID from placebo.

5.2.3.3. Apremilast-exposure Period

The safety analyses for the Apremilast-exposure Period will be based on the apremilast subjects as treated population, which includes all subjects who are randomized to (at Week 0/Visit 2) or treated with (at Week 16/Visit 7) apremilast 30 mg BID, and receive at least one dose of apremilast after randomization or Week 16. All subjects will be included in apremilast 30 mg BID dose group.

5.3. Baseline Definitions

For efficacy analysis and summary of baseline disease characteristics data, baseline is defined as the last value measured prior to or at the randomization visit.

For safety analysis, baseline is defined as the last value measured prior to or on the day of the first dose of IP in the summaries for the Placebo-controlled Phase, and defined as the last value measured prior to or on the start day (defined in Section 5.1, ie, the first apremilast dose date) of the Apremilast-exposure Period in the summaries for the Apremilast-exposure Period. For subjects who are randomized but do not take any study medication, baseline for the Placebo-controlled Phase is defined as the last value measured prior to or on the day of the randomization.

5.4. Time Points

Time points in all analyses are based on the remapped visits/study weeks using the following visit mapping algorithm, which may or may not be the same as the visits/study weeks as recorded in the database.

Post baseline time points in all analyses will be captured based on analysis visit window (range of study days) around the target day for each analysis visit, based on the actual day of evaluation relative to a reference date. Appropriate dates will be used to calculate the study day, e.g., date of measurement or date of specimen collection will first be used, and then the date of visits/study weeks as recorded in the database will be used. If there are multiple measurements within a time point based on the study day, then the non-missing value from the closest measurement to the planned study day will be used for that visit. If the value at a scheduled visit is missing and there is no value available within the time window based on the study day, the value at the study week will be missing.

Table 2: Table for Visit Mapping for by Time Point Analysis

Analysis Visit	Target Day	Visit Window
Baseline	1	≤ 1
Placebo-controlled Phase		
Week 2	15	2 – 21
Week 4	29	22 – 42
Week 8	57	43 – 70
Week 12	85	71 – 98
Week 16	113	99 – End of Phase
Apremilast Extension Phase		
Week 20	141	Start of Phase – 154
Week 24	169	155 – 196
Week 32	225	197 – End of Phase

Note: Target day and visit window are relative to the date of Visit 2/Week 0 (Day 1) for randomization. Definitions for baseline and start or end of the phases are specified in Section 5.1 and 5.3 for both efficacy and safety analysis.

Time points in the analyses or summaries of efficacy data over time include the scheduled study weeks per protocol, the end of a study phase, and the observational follow-up visit. Appropriate dates (e.g., date of measurement or date of specimen collection) will first be used to ensure only data (including data from scheduled, unscheduled, discontinuation, and observational follow-up visits) measured or collected within the specific analysis phase (as defined in Section 5.1) being analyzed or summarized are included, and then the visits/study weeks as recorded in the database will be used to assign one value (possibly missing) to each time point at the subject level. It is possible that multiple assessment values will fall into the same visit window. The following rule may be used to select the unique value for that analysis visit:

1. Among all assessments in the same visit window for the analysis visit, select the value with the assessment date closest to the target day of the analysis visit;

2. If the relative days from 2 assessments are equally close to, but on different sides of the target day, then the latter assessment will be used for that analysis visit;
3. If multiple assessments are available on the same relative day, then the highest value of these assessments will be used for that relative day.

The time points for summaries of safety data (laboratory parameters, vital signs and weight) are based on study week/visit for the Placebo-controlled Phase. For the Apremilast-exposure Period, the scheduled study weeks for placebo subjects who are treated with apremilast 30 mg BID at Week 16/Visit 7 will be mapped to reflect the study weeks relative to the first dose of apremilast (see table below).

Table 3: Adjustment and Mapping of Study Weeks for Placebo Subjects who are Treated with Apremilast 30 mg BID after Week 16 in Summary of Safety Data over Time

Original Visit	Re-Mapped Visit for subjects initially randomized to placebo
Week 16 (Visit 7)	Week 0 (Baseline)
Week 20 (Visit 8)	Week 4
Week 24 (Visit 9)	Week 8
Week 32 (Visit 10)	Week 16

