| Return and count IP tablets                                   | -         | -                                  | -               | X               | X               | X                | X                | X                | X                          | X                | -   | -                       |

Abbreviations: BMI = body mass index; CCI [REDACTED]; CXR = Chest Radiograph; DLQI = The Dermatology Life Quality Index; ECG = Electrocardiogram; ET = Early Termination Visit; FCBP = females of childbearing potential; CCI [REDACTED]

CCI IP = Investigational Product; NRS = Numeric Rating Scale; CCI [REDACTED] ScPGA = Scalp Physician Global Assessment; CCI [REDACTED] TB = tuberculosis testing; CCI [REDACTED]

a All baseline assessments must be completed prior to randomization and dispensing of IP.

b Visit 10 will serve as the Early Termination Visit for any subject who prematurely discontinues from the study.

c All subjects who complete the study or discontinue the study early will be asked to enter the Four-week Post-treatment Observational Follow-up Phase.

d Written informed consent will be obtained by the Principal Investigator or designee prior to performing any study assessments.

e CXRs taken within 12 weeks prior to screening will be accepted. CXRs should be performed as indicated by local treatment guidelines or practice for monitoring while on immunosuppressive/immunomodulatory therapy. If such guidelines are not available/applicable, routine CXRs should be performed as per the Table of Events or when clinically indicated.

f The QuantiFERON® Gold test should be used for TB testing in lieu of the tuberculin skin test (TST) or purified protein derivative (PPD) test, if possible.

g FCBP: Serum pregnancy tests will be performed at the Screening and Early Termination/Last Treatment Visit. Urine dipstick pregnancy test(s) will be performed at baseline, prior to dosing. An unscheduled pregnancy test should be administered if the subject has missed a menstrual period. The Investigator will educate all FCBP about the options for and correct use of contraceptive methods at the Screening and Baseline Visits and at any time when a FCBP's contraceptive measures or ability to become pregnant changes.

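### SAP 5.4 gives two conflicting rules for assigning efficacy values to visits, so some early-termination scores, including ScPGA scores from Day 99, fill a scheduled week under one rule and none under the other

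*SAP*

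**What the plan says.** SAP 5.4 opens with a general rule: "Time points in all analyses are based on the remapped visits/study weeks using the following visit mapping algorithm". It adds that the result may differ from the visit in the database. Table 2 gives the day windows; the Week 16 row has target Day 113 and window "99 – End of Phase".

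A later paragraph of 5.4 deals with efficacy over time. Its time points are "the scheduled study weeks per protocol, the end of a study phase, and the observational follow-up visit". Dates are used first, but only to keep data that fall inside the analysis phase, and discontinuation visits are expressly included. After that, "the visits/study weeks as recorded in the database will be used to assign one value (possibly missing) to each time point".

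The text then returns to windows. "The following rule may be used to select the unique value for that analysis visit", and its first step is: "Among all assessments in the same visit window for the analysis visit, select the value with the assessment date closest to the target day".

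Protocol Table 3, footnote b, fixes the visit number: "Visit 10 will serve as the Early Termination Visit for any subject who prematurely discontinues from the study". Visit 10 is the Week 32 column. SAP 5.1.1 ends the placebo-controlled phase on the discontinuation visit day for subjects who stop at or before Week 16, so the ET assessment lies inside that phase.

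**The concern.** The efficacy paragraph is the more specific text and nothing ranks it below the general rule. Two competent programmers could build different efficacy datasets from the same SAP.

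The difference is not confined to badly mistimed visits. It touches ordinary dropouts, because an ET score recorded as Visit 10 matches no Week 2, 4, 8, 12 or 16 label. For the primary endpoint, an ET ScPGA on or after Day 99 is the observed Week 16 outcome under the windows. Under the recorded visit the Week 16 value is missing, so it is multiply imputed in the primary analysis and set to non-response in the NRI analysis. The NRI sensitivity analysis inherits the ambiguity and cannot resolve it.

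There is also a mismatch with SAP 7, which does not count a subject with a termination visit in the Week 16 window as an early discontinuation. Under the recorded-visit rule such a subject could have no Week 16 primary value although a score was collected.

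**Working it through.** **1. The plan's own figure, as a yardstick.** SAP 4.4 has 300 subjects at 2:1, response 38% versus 20%, two-sided 0.05, power 90%. The pooled rate is (200 × 0.38 + 100 × 0.20)/300 = 0.32. The null SE is √(0.32 × 0.68 × (1/200 + 1/100)) = 0.0571. The alternative SE is √(0.38 × 0.62/200 + 0.20 × 0.80/100) = 0.0527. Power = Φ[(0.18 − 1.96 × 0.0571)/0.0527] = 90.2%, which reproduces the stated 90%.

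**2. Where the two rules differ.** Take each possible ET day from 2 to 112, with earlier scheduled visits on their target days and Week 16 due on Day 113. Apply the Table 2 windows and the closest-to-target rule:

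| Week (window, target) | ET score selected | Scheduled visit closer |
|---|---|---|
| 2 (2-21, 15) | Days 2-15: 14 | Days 16-21: 6 |
| 4 (22-42, 29) | Days 22-29: 8 | Days 30-42: 13 |
| 8 (43-70, 57) | Days 43-57: 15 | Days 58-70: 13 |
| 12 (71-98, 85) | Days 71-85: 15 | Days 86-98: 13 |
| 16 (99-end, 113) | Days 99-112: 14 | none |
| Total of 111 | 66 (59%) | 45 (41%) |

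If the ET visit is labelled only Visit 10, the recorded-visit rule fills a scheduled week on none of the 111 days. The rules therefore disagree on 66 days and agree on 45. If all scheduled visits run 4 days early they disagree on 78 of 107 days (73%); if 4 days late, on 86 of 115 (75%).

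**3. Week 16 values affected.** The documents give no dropout rate. Assume a fraction d of subjects terminates early, spread evenly over Days 2-112. The expected number is 300 × d × 14/111, and the largest possible change in an arm's response rate is 100 × d × 14/111 points:

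| d | Week 16 values | Maximum change in an arm |
|---|---|---|
| 5% | 1.9 | 0.6 points |
| 10% | 3.8 | 1.3 points |
| 20% | 7.6 | 2.5 points |

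With visits 4 days early or late the share 14/111 becomes 10/107 or 18/115. That gives 2.8 to 4.7 values at 10% and 5.6 to 9.4 at 20%. A simulation with early adverse-event and later lack-of-efficacy dropout gave 3.2, 4.8 and 5.8 values at 10%, 15% and 20%. Roughly 3 to 8 of 300 is a fair summary.

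**4. Effect on NRI power.** Suppose the affected subjects respond at the planned rates and are all set to non-response. Both rates are then multiplied by 1 − d × 14/111, and power becomes 89.6% at d = 10% and 89.0% at d = 20%.

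**The case against.** The strongest reply is that 5.4 contains one stray sentence and not two equal rules. Much of this stands. The opening rule covers all analyses and foresees disagreement with the recorded visit. The text right after the disputed sentence selects within a window. SAP 6.3 imputes at scheduled analysis visits, which is Table 2's term, where Protocol 9.6.1.1 speaks of scheduled assessments. SAP 7 treats a termination visit in the Week 16 window as the windows would. Section 5.4 also uses the recorded visit's date as a fallback for the study day, so the disputed sentence may be a garbled form of that fallback. All this shows likely intent. It does not remove a sentence that says something else.

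Stronger readings that a reader might draw are not supported:

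- *Every ET score is at stake.* It is not. With a Week 12 visit on Day 85 and ET on Day 95, both fall in window 71-98, Day 85 is selected, and the ET score fills no scheduled week under either rule.
- *The scores are lost altogether.* The efficacy paragraph has an end-of-phase time point and includes discontinuation data, and SAP 6.5.4 and 6.5.6 use an end-of-phase LOCF value. The score can still be used there, and probably in the LOCF sensitivity analysis.
- *The result is biased in a known direction.* In the simulation the mean change in the treatment difference ran from −0.3 to +0.2 points. Its SD of 0.6 to 1.0 points is no evidence of an effect of the rule. The simulation used 10 imputations, and re-seeding alone at 10% missing and a 20% imputed response rate gives √(2/10 × 0.16 × (20/200² + 10/100²)) = 0.7 points, or 1.0 at 20% missing.
- *The choice will be made unblinded.* SAP 2 requires sign-off before the Week 16 unblinding. Signing does not settle the ambiguity, but nothing shows that it would be settled with knowledge of treatment.

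That the database labels ET only as Visit 10 is inferred from the Table of Events; the case report form is not available.

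**Conclusion.** Wrong as written: an internal contradiction in SAP 5.4 that reaches the primary endpoint, with modest impact. ET scores with no closer scheduled visit in their window are kept for a scheduled week under one rule and not under the other. For the Week 16 ScPGA this concerns ET visits from Day 99 up to the Week 16 visit. At an assumed 10-20% early termination, about 3 to 8 of 300 primary values are affected. With evenly spread ET timing and on-target visits, that is at most 1.3 to 2.5 points on an arm's response rate, against a planned difference of 18 points and a planning SE of 5.3. The counts depend on the assumed rate and timing of dropout and on the ET visit carrying no placebo-phase week label. The case for correction is that the primary dataset should be uniquely defined and that the affected subjects are dropouts, not that the trial's conclusion is shown to be at risk.

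**What to change.** Before Week 16 unblinding, amend SAP 5.4 in three places:

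- Delete the sentence that assigns efficacy values by recorded visit, or limit it to assessments with no usable date.
- State that the Table 2 windows, counted from the Visit 2 date as the table note says, assign every efficacy assessment within the phase, including unscheduled and ET visits.
- In the sentence introducing the selection rule, change *may* to *will*.

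The cost is a few lines of SAP wording. No new data are needed, and the planned sample size and power do not change.

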6. STATISTICAL METHODOLOGY FOR EFFICACY

6.1. General Approaches to Efficacy Analysis

All efficacy evaluations will be conducted using the ITT population. Supportive analysis of the primary efficacy endpoint using the PP population will be conducted.

The summary and analyses of the primary and secondary endpoints evaluated at or prior to Week 16 will be performed by treatment (placebo vs. apremilast 30 mg BID). Statistical comparisons will be made between apremilast 30 mg BID and placebo; the null hypothesis is that the effects of the two treatments (i.e., placebo vs. apremilast 30 mg BID) have no difference.

Descriptive statistics (n, mean, SD, median, Q1, Q3, min, max) will be presented for appropriate endpoints at specified time points. Specifically, for continuous variables, descriptive statistics for baseline and change (or percentage change) from baseline will be provided. Categorical variables will be summarized with frequency tabulations; shift tables will be provided when appropriate.

For discrete variables, the response rate and its 95% confidence interval (CI) will be calculated by treatment. Treatment difference will be tested using the Cochran-Mantel-Haenszel (CMH) test adjusting for the stratification factor at randomization (baseline ScPGA score moderate (3) or severe (4)) for the Double-blind Placebo-controlled Phase. The difference of response rate (apremilast 30 mg BID - placebo) and its 95% CI as well as the p-value will be produced using CMH method.

The continuous endpoints will be analyzed using the analysis of covariance (ANCOVA) model with treatment group and stratification factor as independent variables and the baseline value as a covariate variable. SAS Proc Mixed will be used for the analysis. The least square means (LS mean) with 95% CI for each treatment and difference of LS mean (apremilast 30 mg BID - placebo) with 95% CI as well as the p-value will be provided.

For the primary and the secondary efficacy endpoints, the primary approach in handling missing data will be the multiple imputation (MI) methods. Statistical outputs from the imputed complete data sets will be combined in making statistical inferences.

Efficacy results will be considered statistically significant after consideration of the strategy for controlling the Type I error rate that is described in Section 6.2. All statistical tests will be two-sided and be conducted at the 0.05 significance level, and p-values will be reported.

6.2. Multiplicity Adjustment

The primary and secondary efficacy endpoints will be hierarchically ranked for testing in order to control the overall type I error rate in claiming statistical significance at the 2-sided 0.05 significance level. Specifically, for the primary efficacy endpoint (ScPGA response at Week 16), if the 2-sided p-value from the comparison between apremilast 30 mg BID and placebo is below 0.05, the outcome will be considered statistically significant and apremilast 30 mg BID will be declared effective. For any secondary endpoint, statistical significance will be claimed only if its 2-sided p-value is below 0.05 and tests for the primary endpoint and all previous secondary endpoints are significant at the 2-sided 0.05 level. The proposed test sequence for the primary and secondary efficacy endpoints is listed as the following:

- Proportion of subjects with ScPGA score of clear (0) or almost clear (1) with at least a 2-point reduction from baseline at Week 16
- Proportion of subjects with ≥ 4 -point reduction (improvement) from baseline in the whole body itch NRS score at Week 16
- Proportion of subjects with ≥ 4 -point reduction (improvement) from baseline in the scalp itch NRS score at Week 16
- Proportion of subjects with ≥ 4 -point reduction (improvement) from baseline in the whole body itch NRS score at Week 12
- Proportion of subjects with ≥ 4 -point reduction (improvement) from baseline in the scalp itch NRS score at Week 12
- Proportion of subjects with ≥ 4 -point reduction (improvement) from baseline in the whole body itch NRS score at Week 8
- Proportion of subjects with ≥ 4 -point reduction (improvement) from baseline in the scalp itch NRS score at Week 8
- Proportion of subjects with ≥ 4 -point reduction (improvement) from baseline in the whole body itch NRS score at Week 4
- Proportion of subjects with ≥ 4 -point reduction (improvement) from baseline in the scalp itch NRS score at Week 4
- Proportion of subjects with ≥ 4 -point reduction (improvement) from baseline in the whole body itch NRS score at Week 2
- Proportion of subjects with ≥ 4 -point reduction (improvement) from baseline in the scalp itch NRS score at Week 2
- Change from baseline in DLQI total score at Week 16

6.3. Analyses of Primary Efficacy Endpoint

The primary endpoint is the proportions of subjects who achieving ScPGA response at Week 16 (defined as ScPGA score of clear [0] or almost clear [1] with at least a 2-point reduction from baseline at Week 16). The primary endpoint will be analyzed using the ITT population. A sensitivity analysis will be performed using the PP population.

The treatment difference between apremilast 30 mg BID and placebo will be compared using CMH test adjusting for the stratification factor at randomization. The 2-sided p-values from the CMH test, the adjusted treatment difference in proportion using the weighted average of the treatment differences across the strata with the CMH weights, along with the associated 2-sided 95% CIs using a normal approximation to the weighted average will be provided ([Mehrotra and Railkar, 2000](#)). Missing values at Week 16 will be imputed using the multiple imputation (MI) method ([SAS Institute Inc. 2011](#)) as the primary analysis, with sensitivity analysis using the last observation carried forward (LOCF) method and the non-responder imputation (NRI) method.

The SAS procedure MI will be used to impute missing ScPGA scores at the scheduled analysis visits in the Placebo-controlled Phase (Weeks 0 to 16) to create M=25 complete data sets. The missing data patterns will be checked by treatment and stratification factor at Baseline (Week 0), and Weeks 2, 4, 8, 12 and 16. If there are non-monotone missing patterns, two separate imputation procedures will be used to complete the imputation process.

In the first step, the Markov Chain Monte Carlo (MCMC) method will be used to impute missing scores by treatment and stratification factor to create M=25 imputed data sets with monotone missing patterns. The minimum and the maximum values for imputation will be 0 and 4, which correspond to the lowest and the highest ScPGA scores. The seed will be set to 804529, the imputed values will be rounded to integers and a single chain will be used to produce imputations. In case there are convergence issues, a simple model will be used to impute the missing scores by treatment, with further simplification by dropping both treatment and stratification factor in imputation model if necessary.

In the second step, the predictive mean matching method will be used to impute the remaining missing values for the 25 data sets with monotone missing patterns. The MONOTONE REGPMM statement will be used with seed 447159. The missing values at each visit will be imputed based on treatment, stratification factor, and ScPGA scores at baseline and previous visits. The number of closest observations to be used in the selection will be K=2.

After the completion of imputation, the same CMH method will be used to analyze the 25 complete data sets and the SAS procedure MIANALYZE will be used to combine the results for the statistical inferences.

In summary, the primary analysis will be performed for ITT population using the MI method for treating missing values. Supportive analyses will be performed for: (1) ITT population treating missing values using the LOCF method, (2) ITT population treating missing values using the NRI method, (3) PP population using the MI method for treating missing values. In addition, analyses using CMH test adjusting for the stratification factor at randomization and pooled site will be performed for ITT population using MI method for imputing missing values.

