The study will also investigate the efficacy of apremilast 30 mg BID, compared with placebo, in the improvement of itch. The data from the two pivotal Phase 3 studies of apremilast in subjects with moderate to severe plaque psoriasis (Study PSOR-008 and Study PSOR-009) demonstrated improvement in itch severity using a Visual Analog Scale (VAS). In this study, improvement of itch will be assessed using Numeric Rating Scales (NRS) as these are considered to have better reliability and precision, and lesser potential for missing values, than the VAS (Phan, 2012). The first secondary endpoint will be the proportion of subjects with  $\geq 4$ -point reduction (improvement) from baseline in the Whole Body Itch NRS score at Week 16. It is anticipated that approximately 80% of the subjects would be evaluable for this analysis, based on prior experience in Studies PSOR-008 and PSOR-009 as well as other clinical trials in moderate to severe plaque psoriasis (Griffiths, 2015).

Eligible subjects will be randomized 2:1 to receive either apremilast 30 mg BID or placebo in order to reduce exposure to placebo without greatly increasing numbers of subjects exposed to IP, while maintaining the statistical power of the study. Randomization will be stratified by baseline ScPGA score in order to ensure balance between treatment arms with respect to baseline severity of scalp psoriasis.

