4.4. Sample Size Determination

The sample size estimation is based on the results of the Phase 3 and 3b studies, including CC-10004-PSOR-008, PSOR-009 and PSOR-010 which demonstrated positive treatment effects between apremilast 30 mg BID and placebo in the proportion of subjects achieving ScPGA response at Week 16 (range 18% to 29%). Approximately 300 subjects will be randomized in a 2:1 ratio to apremilast 30 mg BID or placebo. With this sample size, a chi-square test at the 2-sided 0.05 significance level will have 90% power to detect a minimum treatment difference of 18% (38% for apremilast 30 mg BID versus 20% for placebo) between the two arms for

proportions of subjects achieving ScPGA response at Week 16 (defined as ScPGA score of clear [0] or almost clear [1] with at least a 2 point reduction from baseline at Week 16).

If at least 60% of the approximate 300 randomized subjects would be evaluable for the whole body itch NRS analysis, the subset sample size of 180 subjects will provide 90% power to detect a treatment difference of 25% (45% for apremilast 30 mg BID and 20% for placebo) in the proportion of subjects with ≥ 4 -point improvement from baseline in the whole body itch NRS score.

CELGENE PROPRIETARY INFORMATION

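### The SAP's last imputation fallback lets treatment be dropped from the step that fills intermittent Week 2 to 12 itch gaps; the effect is conditional and small, and one wording change removes it

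*SAP*

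**What the plan says.** SAP 6.4.1 describes two imputation steps for whole body and scalp itch NRS, in the same terms as SAP 6.3 uses for ScPGA.

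- **Step 1 (MCMC)** is run only if gaps are non-monotone. It is to "impute missing scores by treatment and stratification factor to create M=25 imputed data sets with monotone missing patterns". If convergence fails, the first fallback is a model by treatment. The last is reached "with further simplification by dropping both treatment and stratification factor in imputation model if necessary". No convergence criterion is given.
- **Step 2 (predictive mean matching)** fills what is still missing. Its model contains treatment, stratum, baseline and earlier visits, and it has no fallback.

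SAP 6.4.2 repeats the fallback for DLQI. Protocol 9.6.1.1, extended to itch by 9.6.1.2, describes the same two steps without any fallback.

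SAP 6.2 ranks twelve tests in a fixed sequence. Ten are itch tests, and eight of those are at Weeks 12, 8, 4 and 2. The closing summary of the itch analyses in SAP 6.4.1 confines the LOCF and NRI analyses to Week 16; Protocol 9.6.1.2 sets no such limit.

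**The concern.** An imputation model that omits treatment assumes that, given a subject's other scores, the arms do not differ at the missing visit. Values filled under that assumption pull the comparison away from what the observed data show, and in this trial the comparison is the estimand.

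For itch at Weeks 2 to 12 nothing later corrects this, because step 2 leaves step-1 values as they are. These visits carry ranked tests in which one failure stops every later claim, including DLQI. With the LOCF and NRI analyses confined to Week 16, no planned missing-data check would show how far an earlier result depended on the branch.

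**Working it through.** **1. Which tests take values directly from step 1.** Step 1 fills only what is needed for a monotone pattern, that is, a missed visit followed by an observed one.

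| Ranked test | Filled in step 1? | Treatment can be dropped? |
|---|---|---|
| ScPGA, Week 16 | No: last visit of the phase, so step 2 | No |
| Itch (two scales), Week 16 | No: step 2 | No |
| Itch (two scales), Weeks 12, 8, 4, 2 (8 tests) | Yes, if a later visit is observed | Yes, in the last fallback |
| DLQI, Week 16 | No: step 2 | No |

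Week 16 values can be touched only indirectly, through step-1 values used as predictors in step 2.

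**2. The plan's own power figures (SAP 4.4).** Formula: power = Φ[(Δ − 1.96·SE0)/SE1], with SE0 from the pooled rate and SE1 from the separate rates.

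- Primary, "38% for apremilast 30 mg BID versus 20% for placebo", 200 and 100 subjects: SE0 = √(0.32×0.68×0.015) = 0.0571; SE1 = √(0.2356/200 + 0.16/100) = 0.0527; power 90.2%. The stated 90% is reproduced.
- Itch, "45% for apremilast 30 mg BID and 20% for placebo", 120 and 60 subjects: SE0 = √(0.3667×0.6333×0.025) = 0.0762; SE1 = √(0.2475/120 + 0.16/60) = 0.0688; power 92.8%. The stated 90% at 180 subjects is matched if a continuity correction is used (required N = 180; without it, 165).

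**3. Upper bound on attenuation.** Suppose a fraction m of values is filled from the pooled response rate, with no use of the subject's other visits. The difference becomes Δ(1 − m). The Week 16 planning rates are applied here to earlier visits, and m is assumed.

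| m | Difference (points) | Power, N = 180 | Power, N = 240 |
|---|---|---|---|
| 0 | 25.0 | 92.8% | 97.9% |
| 1% | 24.75 | 92.3% | 97.6% |
| 5% | 23.75 | 89.8% | 96.4% |
| 10% | 22.5 | 86.1% | 94.3% |

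N = 240 is 80% of 300; Protocol 1.3.2 expects that "approximately 80% of the subjects would be evaluable for this analysis".

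**4. Using the subject's other visits, as MCMC does.** Large-sample simulation: 600,000 subjects generated, 2:1, baseline NRS at least 4 retained. One visit is imputed from all others by normal regression, rounded and limited to 0–10. Assumed SD is 2.5, placebo means fall from 7 to 5.4, and treatment effects at Weeks 2 to 16 are 1.2, 1.6, 1.8, 2.0 and 2.0. Entries are the response difference with treatment dropped minus the difference with imputation by treatment, in points.

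| Adjacent-visit correlation | Week 2, 5% / 10% gaps | Week 12, 5% / 10% gaps |
|---|---|---|
| 0.3 | -0.16 / -0.46 | -0.53 / -1.04 |
| 0.5 | -0.15 / -0.36 | -0.34 / -0.69 |
| 0.7 | -0.13 / -0.29 | -0.16 / -0.39 |

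Example (0.3, Week 12, 10%): 24.09 − 25.13 = -1.04; with no missing data the difference was 25.30.

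**5. Dependence on onset.** Same type of simulation with subject SD 1.8 and residual SD 1.5 (between-visit correlation 3.24/5.49 = 0.59) and different assumed onset shapes, 5% / 10% gaps:

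- No Week 2 effect, real later effects: Week 2 +0.27 / +0.49; Week 12 -0.63 / -1.43.
- Effect growing from Week 2: Week 2 +0.08 / +0.18; Week 12 -0.51 / -0.95.
- Constant effect from Week 2: about -0.2 to -0.5 at each of the four visits.
- No effect at any visit: about 0 throughout.

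Imputation by treatment stayed within 0.2 points of the full-data difference in both sets.

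**6. What +0.5 at a null Week 2 would do.** With 160 and 80 subjects and an assumed 15% response in both arms, SE = √(0.15×0.85×(1/160 + 1/80)) = 4.9 points. The shift is 0.5/4.9 = 0.10 SE, and the two-sided error becomes P(Z > 1.96 − 0.10) + P(Z < −1.96 − 0.10), about 5.1% instead of 5.0%.

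**The case against.** The strongest reply is that the branch may never be used. It needs non-monotone gaps, then failure of the model by treatment and stratum, then failure of the model by treatment. That last model fits six scores on about 60 to 80 placebo and 120 to 160 apremilast subjects, and nothing suggests it would fail. The visit windows in SAP 5.4 adjoin (Days 2–21, 22–42, 43–70, 71–98) and unscheduled visits count, which should keep gaps few. All of this stands, and it is why the point is minor. It does not justify keeping an option that can only harm the comparison.

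Three stronger readings are tempting, and the documents do not support them.

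- *The primary result is at risk.* The quoted sentence does stand in SAP 6.3, but a missing Week 16 ScPGA score is filled in step 2 with treatment in the model. The same holds for DLQI at Week 16.
- *The ScPGA model is bound to fall through to the treatment-free version.* Within a stratum baseline ScPGA is constant, so the covariance matrix in the first-choice model is singular. But the by-treatment fallback lets baseline vary between 3 and 4 and so removes that singularity. Baseline itch NRS is not fixed by the stratum at all.
- *The branch would create a false early onset of itch relief.* The sign at Week 2 depends on the onset profile: upward when the effect builds over time, downward when it is present from the start. Even the upward case barely moves the error rate, and Week 2 is tested only after every ranked test at Weeks 16, 12, 8 and 4 has succeeded.

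**Conclusion.** The point holds as a minor wording defect in SAP 6.4.1. As written, the plan allows intermittent itch gaps at Weeks 2, 4, 8 and 12 to be filled without treatment in the model, and those values would feed eight ranked tests that have no planned LOCF or NRI check.

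If the branch were used with 5 to 10% intermittent gaps, the Week 12 difference would shrink by about 0.3 to 1.4 points across the onset profiles, and by as little as 0.2 where visits correlate strongly. A loss of 1.25 points on the planning rates takes power from 92.8% to 89.8% at 180 subjects, or from 97.9% to 96.4% at 240. The Week 2 difference would move by about -0.4 to +0.5 points.

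The gap rates, trajectories, correlations and the use of Week 16 planning rates at earlier visits are all assumptions; the documents give none of them for Weeks 2 to 12. The structural finding needs none of them. Attenuation at Week 12 appeared in every profile with a real effect, whereas no general direction can be claimed for Week 2.

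**What to change.** In SAP 6.4.1, delete the option to drop treatment and keep treatment in every fallback: drop the stratum first, then simplify the covariance within treatment arm, for example with a ridge prior. Make the same edit in 6.3 and 6.4.2 for consistency. In the same edit it would help to state what counts as a convergence failure, and to extend the itch LOCF and NRI analyses to Weeks 2 to 12, which Protocol 9.6.1.2 does not limit to Week 16.

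The change is to SAP wording only. It needs no new data and no change in sample size, and should be made before the Week 16 data are unblinded, when SAP section 2 requires the plan to be final.
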